10.21.4 AE Duration

The AE duration (expressed in days) will be defined as:

- AE stop date – AE start date + 1 day.

The duration will not be derived in case of partial or missing start or stop date.

Based on the above value the AE duration will also be categorized as follows:

- 1-7 days,
- 8 to 14 days,
- 15 to 28 days,
- 28 to 42 days,
- 43 to 61 days,
- 61 days,
- Ongoing,
- Indeterminate.

If AE stop date is missing and the outcome of the AE is “Not recovered, Not resolved”, the AE will be categorized as “Ongoing”.

If the AE start date is partial or missing and the AE is not considered as “Ongoing”, the AE will be classified as “Indeterminate”.

10.22 Laboratory data

Strip-sign handling

In cases a hematology or chemistry value is recorded as ‘>x’ or ‘’, the value will be imputed as “x” to perform summary statistics but the strip sign will be presented in individual data listings.

10.23 Columbia Suicide Severity Rating Scale (C-SSRS)

The C-SSRS scale is composed of 11 items answered Yes or No. Ten of them are ordered in categories as described below to determine the studied endpoints.

5 subtypes of suicidal ideation:

- Category 1 – Wish to be Dead,

- Category 2 – Non-specific Active Suicidal Thoughts,
- Category 3 – Active Suicidal Ideation with Any Methods (Not Plan) without Intent to Act,
- Category 4 – Active Suicidal Ideation with Some Intent to Act, without Specific Plan,
- Category 5 – Active Suicidal Ideation with Specific Plan and Intent.

5 subtypes of suicidal behavior:

- Category 6 – Preparatory Acts or Behavior,
- Category 7 – Aborted Attempt,
- Category 8 – Interrupted Attempt,
- Category 9 – Actual Attempt (non-fatal),
- Category 10 – Completed Suicide.

Last item:

- Self-injurious behavior without suicidal intent.

The C-SSRS also includes a suicidal ideation intensity rating from 1 (least severe) to 5 (most severe).

The following composite endpoints will be assessed based on the categories described above:

- Suicidal ideation (Yes/No): is Yes if one of the categories from 1 to 5 is answered Yes,
- Suicidal behavior (Yes/No): is Yes if one of the categories from 6 to 10 is answered Yes,
- Suicidal ideation or behavior (Yes/ No): is Yes if one of the categories from 1 to 10 is answered Yes,
- Self-injurious behavior without suicidal intent (Yes /No): is Yes if this question is answered Yes.

The following scores will be derived as follows:

- Suicidal ideation score is rating from 1 to 5 the most severe suicidal ideation category answered Yes and is assigned to 0 if categories 1 to 5 are answered No,
- Suicidal ideation intensity rating score (0 to 25) will be defined as the sum of the 5 features described below (ranging from 0 to 5, 0 being the least severe and 5 being the most severe) rated with respect to the most severe type of ideation category,
 - Frequency,
 - Duration,
 - Controllability,
 - Deterrents,
 - Reason for ideation.

Comparative endpoints will also be defined as described below:

Treatment emergent outcomes will include any events that first emerge or worsen, whereas emergent outcomes will refer to outcomes that first emerge.

- Treatment-emergent suicidal ideation compared to recent history (not using C-SSRS taken during screening):
 - Increase from baseline in suicidal ideation score,
 - Increase from last on-treatment visit to follow-up (FU) visit,
- Treatment-emergent serious suicidal ideation compared to recent history (not using C-SSRS taken during screening):

- Increase in suicidal ideation score from a baseline (0-3) to (4-5),
- Increase in suicidal ideation score from last on-treatment visit (0-3) to FU visit (4-5),
- Emergence of a serious suicidal ideation compared to recent history (not using C-SSRS taken during screening):
 - Increase in suicidal ideation score from baseline (0) to (4-5),
 - Increase in suicidal ideation score from last on-treatment visit (0) to FU visit (4-5),
- Emergence of suicidal behavior compared to all prior (using C-SSRS taken at and post screening assessments):
 - Occurrence of suicidal behavior (categories 6-10) post baseline with no screening or baseline suicidal behavior,

No imputation should be done with regards to missing data.

11.0 Interim Analyses

No interim analysis will be conducted.

However, a blinded assessment of the estimate of the variability of the treatment difference will be conducted during the study and the sample size recalculated using this blinded estimate. The study will still be ongoing at time of these blinded analyses and the decision whether or not to increase the sample size will be based on the Sponsor judgment.

This blinded review of the data will take place once, using the first 50% of the patients, from FAS, having completed both treatment periods, and for whom all MAS assessment data are cleaned (no open queries), coded and reconciled.

11.1 Blinded Sample Size Reassessment

The sample size estimate as described in [Section 10.8.2](#) was assuming mean treatment difference of -0.18 and a standard deviation of paired difference of 0.71.

Let d_i denote the difference between Period 2 and Period 1 for Patient i ($i = 1$ to n) when n is the number of patients, at the interim analysis, having completed Period 1 and Period 2 on-treatment and for whom LLMT-6 score (as described in [Section 10.16](#)) can be derived for both treatment periods.

Let \bar{d} is the overall mean of all d_i

When the n patients complete the assessment on the primary endpoint, the variability is estimated by pooling all the patients as follows

$$\hat{\sigma}_{diff}^2 = \frac{1}{(n-1)} \sum_i^n (d_i - \bar{d})^2$$

The re-calculated sample size is given by

$$\hat{N} = \frac{(t_{1-\alpha} + t_{1-\beta})^2}{\delta^2} \hat{\sigma}_{diff}^2$$

That is,

$$\widehat{N} = \frac{(t_{1-\alpha} + t_{1-\beta})^2}{\delta^2} \frac{1}{(n-1)} \sum_i^n (d_i - \bar{d})^2$$

where δ is the target treatment effect size. This re-calculated sample size will be provided to the sponsor to aid decision-making; however the sponsor has the final decision as to whether to increase the sample size and to what number.

11.2 Other Analyses

Baseline efficacy endpoints will be summarised and no other additional analyses are planned during the blinded sample size reassessment.

12.0 Statistical Methods

All analyses will use SAS® version 9.4 or higher. However, pharmacokinetic analyses may be performed using a dedicated software as mentioned in [Section 12.6](#).

Standard Summary Statistics for Continuous and Discrete Variables.

Summaries will be tabulated either per treatment arm or per treatment sequence, and overall (when deemed appropriate), unless otherwise specified.

Unless otherwise noted, **categorical variables** will be summarized using non-missing counts and percentages. Percentage will be using the number of patients (or the number of patients at risk) in the treatment arm/treatment sequence and as appropriate in the analyzed categories as denominator. Percentages will be rounded to one decimal place, except 100% will be displayed without any decimal places and percentages will not be displayed for zero counts.

Odd ratios (ORs) will be provided as appropriate. Odd ratios will be presented with 2 decimal places .

Continuous data will be summarized using the number of non-missing observations (n), mean, standard deviation (SD), median, first quartile (Q1), third quartile 3 (Q3), minimum (Min), and maximum (Max). Minimum and maximum, will be rounded to the precision of the original value. Mean, median, Q1 and Q3 will be rounded to 1 decimal place greater than the precision of the original value. The SD will be rounded to 2 decimal places greater than the precision of the original value. Confidence intervals (CIs), LS means, standard error (SE), geometric mean, geometric SD and coefficient of variation (CV) (%) will be provided as appropriate. Confidence intervals, LS means and geometric mean will be presented with the same precision as the mean value whereas SE and geometric SD will be presented with the same precision as SD and the CV (%) will be presented with 1 decimal place.

Inferential Statistics

P-values will be rounded to 4 decimal places. P-values less than 0.0001 will be presented as “<0.0001” and p-values greater than 0.9999 will be presented as “>0.9999.”

Statistical hypothesis testing will be 2-tailed and carried out at the 5% level of significance. Testing will be performed on the primary endpoint and secondary endpoint as appropriate.

To control for Type 1 error at a 2-sided alpha of 0.05, the primary endpoint and key secondary endpoint will be tested hierarchically, starting with the primary endpoint and followed by the secondary endpoint. No additional adjustments for multiplicity will be made for the other secondary endpoints and for exploratory endpoints although nominal p-values will be presented.

Individual Data Listings

All the listings will be displayed sorted by treatment sequence, patient identifier and date of assessment. They will present age, sex, race and country.

For those listings presenting on-treatment assessment post randomization, treatment arm along with the treatment period will also be displayed. A flag informing whether or not the data are impacted by COVID-19 may also be added.

12.1 Patient Disposition

The number and percentage of patients screened, re-screened, randomized and not randomized along with reason of screen failure will be presented using the Screening Analysis Set.

The number of patients randomized, randomized and treated, randomized and not treated, and the number of patients in each analysis set will be summarized per treatment sequence for the Randomized Analysis set.

The number and percentage of patients will also be summarized for the following patient disposition categories:

1. Completed study drug treatment per protocol
2. Discontinued study drug early and the reason for discontinuation
3. Completed the study including follow-up period
4. Discontinued from the study early and the reason for discontinuation

The table will be presented by treatment sequence, per period and overall using the Randomized Analysis Set and will be repeated for the different subgroups presented in [Table 12.1-1](#).

Table 12.1-1 Subgroups Applied to Patient Disposition

Group Variables	Subgroup	Comments
Sex	Male Female	
Age group	<= 18 years > 18 and ≤ 45 ≥ 46 to ≤ 65 > 65	According to patient 's distribution within age, age group may be differently defined Detailed derivation is given in Section 10.10
Race	White Black or African American Asian American India or Alaska Native Native Hawaiian or Other Pacific Islander Other	According to patient's distribution within race some races may be grouped together
Prior cannabis use	Yes No	
Number of current antispasticity medication	0 1 2 ≥ 3	
Country	Spain UK Czech Republic Poland USA	
Current antispasticity medication use	Yes No	It is derived from concomitant medication form. Current antispasticity medication use status will be "Yes" if a subject chose "Anti-spasticity" category for multiple sclerosis, and if "Anti-

		spasticity" is not chosen, the current antispasticity medication use will be "No"
Region	USA Region Non-USA Region	If country is USA, then region will be "USA Region", and if not USA country, region will be "Non-USA Region"

A cumulative incidence plot of permanent IMP discontinuation due to any reason will be provided by treatment sequence on the Safety Analysis Set. The Time to treatment discontinuation (in days) is defined as the number of days from 1st IMP intake until permanent treatment discontinuation (as detailed in [Section 10.6](#)). Patients who will not permanently withdraw from study drug will be censored to the earliest of last contact date and their date of completion of Period 2, whereas patients lost to follow-up will be censored at their last contact date.

A cumulative incidence plot of study discontinuation due to any reason will be provided by treatment sequence on the Randomized Analysis Set. The Time to study discontinuation (in days) is defined as the number of days from randomization until study discontinuation (as detailed in [Section 10.6](#)). Patients who will not permanently withdrawn from study drug, or lost to follow-up will be censored at the end at their last contact date.

Each cumulative incidence plot will only be provided if more than 5 patients are presenting an event in each treatment sequence (i.e., premature end of treatment, premature study discontinuation).

A tabulation based on the Randomized Analysis Set of the number and percentage of patients randomized at each region, country and center will be presented per randomization sequence and overall.

All patient's disposition data will be listed by treatment sequences.

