## **10 WITHDRAWAL**

In accordance with the Declaration of Helsinki, the ICH Tripartite Guideline for GCP Topic E6(R2), the US Food and Drug Administration (FDA) regulations relating to GCP and clinical trials, the EU Clinical Trials Directive, the EU GCP Directive, and/or other applicable regulations, a patient has the right to withdraw from the study at any time and for any reason, with no obligation to provide a reason, and without prejudice to his or her future medical care by the physician or at the institution.

The patient must be withdrawn from the trial if any of the following apply:

- Administrative decision by the investigator, GW, or a regulatory authority
- Withdrawal of patient consent
- Lost to follow-up

The patient must cease IMP and should remain in the trial if any of the following apply:

- Pregnancy
- Protocol deviation that is considered to potentially compromise the safety of the patient
- Suicidal behavior or ideation of type 4 or 5 during the treatment period, as evaluated with the C-SSRS
- ALT or AST  $> 3 \times$  ULN with the appearance of fatigue, nausea, vomiting, right upper quadrant pain or tenderness, fever, rash, and/or eosinophilia ( $> 5\%$ )
- ALT or AST  $> 5 \times$  ULN
- ALT or AST  $> 3 \times$  ULN **and** (total bilirubin [TBL]  $> 2 \times$  ULN **or** international normalized ratio [INR]  $> 1.5$ )

The patient may be required to cease IMP at the discretion of the investigator and should remain in the trial for any of the following reasons:

- Did not meet eligibility criteria
- Patient noncompliance
- AE (including clinically significant laboratory result) that, in the opinion of the investigator, would compromise the continued safe participation of the patient in the trial
- Any evidence of drug abuse or diversion
- Disease progression (defined as a relapse of MS requiring a change in treatment)

Should a patient request or decide to withdraw from the study, all efforts must be made to complete and report the observations as thoroughly as possible up to the date of withdrawal. Patients withdrawing due to an AE should be followed up according to [Section 12.7](#). All information should be reported on the applicable eCRF pages (refer to [Section 9.2](#)). A Safety Follow-up Visit should take place 7 (+ 3) days after last dose of IMP or after the End of

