12.7.1 Adverse Events

Adverse events (AEs) will be coded using MedDRA 24.0 or higher according to the version in use at time of database lock. All safety analyses of AEs will be performed by actual treatment arm and reported using the Safety Analysis Set. An AE will be considered a TEAE if it first occurs or worsens in severity or seriousness after the first dose of IMP intake and before the last dose date + 15 days.

All AEs will be classified during the pre-treatment period, the 51-day safety on-treatment period or during the follow-up period as follows:

Events that occurred before first IMP intake without worsening or becoming serious after the first IMP dose are classified as **pre-treatment AEs**;

Events that occurred or worsens between first IMP dose and 14 days after IMP last dose are classified as on-treatment AE and are defined as **treatment-emergent AEs** (TEAEs);

- TEAE occurring during 21-day on-treatment safety Period 1 will be considered emergent to actual treatment received during Period 1 (as defined in [Section 10.1.1](#)).
- TEAE occurring during 21-day on-treatment safety Period 2 will be considered emergent to actual treatment received during Period 2 (as defined in [Section 10.1.1](#)).

Events occurring more than 15 days after last dose are classified as **follow-up AEs**.

Consequently, TEAEs will be summarized by treatment arm using the actual treatment received at each given period. Any adverse event occurring during the wash-out period will be linked to the actual treatment arm defined for Period 1, whereas any AEs occurring after last IMP dose will be linked to the actual arm defined at time of permanent study drug discontinuation.

The following events will not be identified as AEs in this study:

- Medical or surgical procedures (e.g., surgery, endoscopy, tooth extraction, etc.). The condition (the “triggering event”) that leads to the procedure are adverse events and will be reported as such.

- Pre-existing conditions present or detected prior to the first dose of study drug that do not worsen during the study.

Counting rules

For incidence reporting, if a patient reported more than one AE that was coded to the same preferred term/system organ class within a given treatment arm, the patient will be counted only once for that specific preferred term/system organ class by treatment arm and the rules defined below will be applied.

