12.7.2.3 Adverse Events of Special Interest

An adverse events of special interest (AESI) is any adverse event of scientific or medical interest to the study medication. The types of AESIs which will be analyzed are presented in **Descriptive presentations of AESIs** will be given for each AESI category on the safety analysis set presenting:

- The number and percentage of patients with at least one treatment-emergent AESI,
- The number and percentage of patients with at least one treatment-emergent AESI by SOC and PT,
- The number and percentage of patients with at least one severe treatment-emergent AESI,

- The number and percentage of patient with at least one serious treatment-emergent AESI,
- The number of and percentage of patients with at least one treatment-emergent AESI leading to permanent IMP discontinuation,
- The number of treatment-emergent AESI,
- The number of severe treatment-emergent AESI,
- The number of serious treatment-emergent AESI,
- The number of treatment-emergent AESI leading to permanent IMP discontinuation,
- The number of unique* treatment-emergent AESI,
- The number of unique* severe treatment-emergent AESI,
- The number of unique* serious treatment-emergent AESI,
- The number of unique* treatment-emergent AESI leading to permanent IMP discontinuation,
- The time to first onset of treatment-emergent AESI categorized as :1-7 day, 8 to 14 days, 15 to 21 days, 21 to 28 days and > 28 days (as described in [Section 10.21.3](#)),

**Unique AESI is defined as any AESI coded with the same PT and having the same date of onset.*

Analysis of time to first onset of AESIs will be conducted by actual treatment arm on the Safety Analysis SAS using the SAS® LIFEEST procedure.

Assuming no carry over effect, Kaplan-Meier plots (estimates) of cumulative incidence of first onset of AESI will be provided by actual treatment arm on the Safety analysis set. The time to AESI onset (in days) is defined as the number of days from 1st IMP intake of the treatment arm (e.g., nabiximols, placebo) the AESI is emergent to (as defined in [Section 12.7.1](#)) until the onset of the AESI (see detailed in [Section 10.21.4](#)).

For patients not known to have experienced an AESI during respectively Period 1 and Period 2:

- Period 1 censoring day is the date of 1st IMP intake during Period 2 minus 1 day for those patients continuing in Period 2 and, the end of study date for those patients who discontinued before Period 2,

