- Period 2 censoring day is the end of study date in the period.

Additionally, for lost to follow-up patients:

- Period 1 censoring day is the earliest date between end of study date in the period and the planned Visit 6 day minus 1 day (Day 30),
- Period 2 censoring day is the earliest date between end of study date in the period and the planned Visit 10 day (Day 58).

To accompany the Kaplan-Meier (KM) plots, summary tables will display the KM estimates of cumulative probabilities (with 95% CI calculated based on the Greenwood method when applicable).

- of patients with an event at a specific time point such as 7, 14, 21, 28 (if applicable) days after 1st IMP intake in the studied period;
- time to first event based on the 10th, 20th, 30th, 40th, 50th (median) and 75th percentiles.

If the estimate of lower bound of the 95% CI is below '0' or the estimate of the upper bound of the 95% CI is over '1', then it will be respectively restricted to '0' and '1'.

The number of patients at risk along with the number and percentage of patients censored and with an event, using the number of patients at risk as denominator to calculate the percentage will also be displayed.

Each Kaplan-Meier plot (estimates) will only be provided if more than 5 patients are presenting an event in each treatment arm.

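### The study-discontinuation curve in SAP 12.1 appears to censor patients lost to follow-up and is keyed to study-drug status, so it would understate discontinuation and disagree with the disposition table

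*SAP*

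**What the plan says.** SAP 12.1 defines the output: "A cumulative incidence plot of study discontinuation due to any reason will be provided by treatment sequence on the Randomized Analysis Set". Time runs from randomization to study discontinuation. SAP 10.6 gives the time formula and refers to 12.1 for the censoring rules, so the rule in 12.1 is the operative one: "Patients who will not permanently withdrawn from study drug, or lost to follow-up will be censored at the end at their last contact date".

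The paragraph before it covers a different plot, permanent discontinuation of study drug. There the treatment of losses is explicit: "whereas patients lost to follow-up will be censored at their last contact date".

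Protocol Section 10 opens its first list with "The patient must be withdrawn from the trial if any of the following apply". One of the three entries is "Lost to follow-up"; the other two are an administrative decision and withdrawal of consent.

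SAP 12.1 also plans a disposition table on the same analysis set and by the same treatment sequences. It counts patients who completed the study, follow-up included, and patients who left early, with the reason. Each cumulative incidence plot is produced only if more than 5 patients per sequence have the event.

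**The concern.** For a curve of leaving the study for any reason, loss to follow-up is one way of having the event. Censoring at last contact assumes that the patient could still leave later and was simply not observed. Under the protocol that patient has already left.

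The rule also sorts patients by the wrong status. The event is leaving the study, but the non-event group is described by whether the patient stayed on study drug. This protocol deliberately separates the two, because patients who stop drug are encouraged to remain to the end of the period.

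At stake is a descriptive retention figure. It would show less attrition than the table beside it, for the same patients and the same analysis set, and a reader would have no stated reason for the gap.

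**Working it through.** The plan gives no numerical result for this curve, so there is none to reproduce. The check has two parts.

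**1. The text**

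| Patient | Protocol 10 and disposition table | Censoring sentence in SAP 12.1 |
|---|---|---|
| Lost to follow-up | Withdrawn from the trial; counted as early discontinuation | Censored at last contact (natural reading) |
| Finishes both drug courses, leaves before Visit 10 | Has not completed the study including follow-up | Censored, because not withdrawn from study drug |
| Stops drug in Period 2, stays to the end of the study | Study completer (the completer set in SAP 9.3.2.5 disregards drug withdrawal) | In neither censored group; no rule given |

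**2. The size**

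Inputs:
- 190 randomized and at least 170 completers (Protocol 13.1, SAP 8.2), so 190 − 170 = 20 leave. With 95 per sequence, that is about 10 in each.
- The number lost to follow-up is not in the documents. I assume 5 or 8 of 20 overall, and 1 to 5 of 10 within a sequence.
- Everyone else is assumed to be followed beyond the last counted event.

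Let n be randomized, w those who leave, and l those of the w who are lost.
- Counting every reason, the curve ends at w/n.
- Censoring the losses, it ends between (w − l)/n, if all losses come after the last counted event, and (w − l)/(n − l), if all come before the first.

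| n | w | l | Any reason | Losses censored |
|---|---|---|---|---|
| 190 | 20 | 5 | 20/190 = 10.5% | 15/190 to 15/185 = 7.9% to 8.1% |
| 190 | 20 | 8 | 10.5% | 12/190 to 12/182 = 6.3% to 6.6% |
| 95 | 10 | 1 | 10/95 = 10.5% | 9/95 to 9/94 = 9.5% to 9.6% |
| 95 | 10 | 2 | 10.5% | 8/95 to 8/93 = 8.4% to 8.6% |
| 95 | 10 | 3 | 10.5% | 7/95 to 7/92 = 7.4% to 7.6% |
| 95 | 10 | 5 | 10.5% | 5/95 to 5/90 = 5.3% to 5.6% |

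In the last row only 10 − 5 = 5 events remain in the sequence. That is not more than 5, so if losses are not events the plot would not be produced at all, although 10 of 95 patients left.

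**The case against.** **The sentence may mean something else.** It is ungrammatical and could be read as censoring patients who were neither withdrawn nor lost, in which case losses would count. That reading cannot be excluded. The explicit rule in the preceding paragraph favours the other one, though it governs a different plot. On either reading the rule still refers to study drug and needs rewriting.

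**The study-drug wording looks carried over from that paragraph.** Probably so, and its net direction is not established. Censoring patients who finish dosing and then leave lowers the curve, but only for departures in the 7 to 10 days between Visit 9 and Visit 10. The patient who stops drug and completes the study has no rule, so the effect there is undefined.

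**No attrition is hidden.** This stands. The table gives every early discontinuation with its reason, and the disposition data are listed. The fault is one plot that disagrees with the table.

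**The plot may never appear.** It depends on the event threshold. Enrollment also stopped early, and the addendum's table for abbreviated reporting, as far as it can be read, does not name the disposition plots.

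**A stronger reading to avoid.** A reader might infer that the Kaplan-Meier curves for adverse events of special interest (SAP 12.7.2.3) are also too low. Patients who stop drug early stay at risk to the end of study, although events count only up to 14 days after the last dose. The documents do not support calling that an error. Suppose a 20% 28-day incidence at constant hazard, with 10% of an arm stopping on Day 3 and staying to Day 28. Their events count to Day 17, so the proportion of treated patients with a treatment-emergent event is 0.9 × 20% + 0.1 × (1 − 0.8^(17/28)) = 18% + 0.1 × 12.7% = 19.27%. The planned curve gives the same 19.27%. Censoring at last dose plus 14 days would instead target a hypothetical on-drug incidence, and would require stopping to be unrelated to risk, which is doubtful when patients stop for adverse events. That is a choice of estimand, and SAP 12.7.2.3 does not commit to the other one.

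**Conclusion.** The point holds for the study-discontinuation plot. As most naturally read, the rule censors patients whom the protocol treats as withdrawn, so the curve would sit too low and disagree with the disposition table. It also leaves drug-stoppers who complete the study without a rule.

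The shortfall depends on how many of those who leave are lost to follow-up, which the documents do not say. With 20 of 190 leaving, it is about 2.5 percentage points if 5 are lost and about 4 if 8 are lost; with none lost it is zero. The conclusion rests on one reading of a garbled sentence, although the case for rewriting it does not.

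The consequence is modest: a conditional, descriptive output, with no bearing on LLMT-6, LLMT-4 or any other tested result.

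**What to change.** Replace the censoring sentence for the study-discontinuation plot in SAP 12.1 with a rule keyed to study status:
- Any early departure from the study is an event, including loss to follow-up, which is dated at last contact.
- Only patients who complete the study, follow-up included, are censored. They are censored at study completion, whatever their drug status.

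Apply the same event definition to the threshold of more than 5 events per sequence, and check that the number of events in each sequence equals the early-discontinuation count in the disposition table.

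The cost is one SAP sentence and a small change to the derivation code, with no new data. The downside is a slightly less favourable descriptive figure.
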